## CHANGES TO THE PROTOCOL

### Protocol Amendment 4 – Summary of Changes:

The primary purpose of Amendment 4 is to add 14 days to the screening period to give subjects more time to complete screening assessments due to extenuating circumstances of the COVID-19 pandemic. The changes to the protocol are listed below.

1. Section 1.2 Study Schematic: the following changes have been made:
    - a. Change: The Screening Visit from “Day -14 to Day -1” to read: “Day -28 to Day -1.”
    - b. Add footnote “a” to the table heading for Final Visit (7 days post-dosing) (+ 3 daya window) that reads: “If circumstances occur such that this visit cannot occur within the specified window, the visit window may be extended to 14 days, after discussion with the Sponsor.”
  2. Section 1.3 Schedule of Study Events: Change: Screening from “Day -14 to Day -1” to read: “Day -28 to Day -1.”
  3. Section 4.1 Overall Design:
    - 2nd paragraph, 2nd sentence: Change: “Subjects may participate in the study for a total of up to approximately 3 to 4 weeks, including a screening period of up to 14 days” to read: “Subjects may participate in the study for a total of up to approximately 6 weeks, including a screening period of up to 28 days.”
    - Add 3rd paragraph: “The final visit window may be extended, due to extenuating circumstances, to 14 days after discussion with the Sponsor.”
  4. Section 5.2: Add exclusion criterion #19: “Has hyponatremia, defined as blood sodium level  $\leq 125$  mmol/L.” Subsequent exclusion criterion renumbered accordingly.
  5. Section 5.4 Screen Failures:
    - 2nd paragraph: Change: “The period from the start of screening related procedures at the Screening Visit to randomization must not exceed 14 days, inclusive of any repeat screening procedures.” to read: “The period from the start of screening related procedures at the Screening Visit to randomization must not exceed 28 days, inclusive of any repeat screening procedures.”
    - 4th paragraph: Change: “Subjects may be rescreened for a subsequent episode of acute HE, provided that the subject was not randomized.” to read: Subjects may be rescreened provided that the subject was not randomized.
  6. Section 8.1 Screening:
    - Heading: Change: “Screening (Day -14 to Day -1)” to read: Screening (Day -28 to Day -1)”
    - Third bullet: Change: “Record medical/surgical history” to read: Record medical/surgical history (including history of exposure to COVID-19).
-

- 
- Last paragraph: Change: "...screening (up to 14 days before Day 1)." to read: "...screening (up to 28 days before Day 1)."
7. Section **8.4 Final Visit (Week 2)**:
- 2nd paragraph: Add: "The final visit window may be extended, due to extenuating circumstances, to 14 days after discussion with the Sponsor."
  - Add: Section **8.9 Provisions for Remote Assessment Methods**  
"For emergency situations where there are extenuating circumstances that prohibit physically coming to the clinical site or when the safety of subjects may be compromised by physical visits to the site, remote assessments may be considered after discussion with the Sponsor."

Other minor edits to text (including updating page headers/footers with current protocol template) were made to the document that did not affect study conduct.

### **Protocol Amendment 3 – Summary of Changes:**

The 3rd amendment was implemented to make minor changes to the inclusion/exclusion criteria and prohibited medications to clarify criteria for and required documentation defining HE to facilitate enrollment in the study based on investigator observations/input during the trial.

1. **Table 1** (Schedule of Study Events):
    - Clarification that C-P and MELD scores do not need to be repeated at the time of confinement (Day -1) as they will be performed at screening (Days -14 to Day -1).
    - Clarification that urinalysis will be performed on Days 1 to 5 (not Days 1 to 6 as for chemistry and hematology laboratories). This change was also made to text in Section **8.3** (Treatment Period [Week 1; Day 1 to Day 5/ET] and Day 6 [Discharge]).
    - Urine pregnancy test added to Day -1 (first day of confinement) for women of child-bearing potential. Text has also been added to Section **8.1** (Screening [Day -14 to Day -1]), Section **8.6.6**, and Section **10.2** (Clinical Laboratory Tests).
  2. Section **3.3** added: Outcome measures are identified to facilitate clinical trial registration and patient access to basic results disclosed on public clinical trial registries.
    - Primary: Number of participants with a change in ammonia at Day 5.
    - Secondary: Number of participants with adverse events or deaths during the study.
  3. Section **5.1** Inclusion Criteria:
    - Inclusion criterion **#4** was changed from "A history of at least 2 or more documented episodes of HE within the last 12 months, with 1 episode within the last 6 months." To read: "A history of at least 1 or more documented episodes of HE within the last 12 months."
    - Inclusion criterion **#5** was changed from "Hyperammonemia at screening." To read: "Hyperammonemia (defined as an ammonia level  $\geq 37$   $\mu\text{mol/L}$ ) at screening."
-

- 
4. Section 5.2 Exclusion Criteria: Exclusion criterion #16 (second bullet) was changed from “Platelet count no more than 50,000 cells/ $\mu$ L” to read “Platelet count no more than 25,000 cells/ $\mu$ L.”
  5. Section 6.5.1 Prohibited Concomitant Therapies (Second bullet) was changed from “Current use of drugs whose plasma concentration may be affected by MNK6106, such as alfentanil, cyclosporine, midazolam, quinidine, metformin, or cimetidine.” To Read: “Current use of drugs whose plasma concentration may be affected by MNK6106, such as alfentanil, cyclosporine, midazolam, quinidine, or cimetidine. Metformin use is permitted at low doses. Doses of metformin > 1,000 mg should be discussed with the medical monitor prior to enrollment.”
  6. Section 10.8 (Stages of Hepatic Encephalopathy According to HESA):
    - Replaced HESA sheet with HESA sheet approved for use in the study and added reference (Hassanein et al, 2008).
    - Added a sentence to describe the new HESA scale with respect to the severity as follows: “It consists of a 5-point scale (Grade 0 to 4), with 4 indicating most severe.”

Other minor issues (document conversion to Accenture StartingPoint Authoring Template, adding references, removing a web address, etc) were addressed; none affected study conduct.

### Protocol Amendment 2 – Summary of Changes

The second amendment to the protocol was implemented to clarify and ensure consistency of text throughout the protocol. Changes to the protocol are summarized below.

1. Section 1, Table 1 (Schedule of Study Events): added MELD score and HESA score limited physical examination to Day 6 (end of confinement); added complete physical examination on Day -1; included collection of concomitant medications/therapies at screening (Day -14 to -1) and on Day -1; removed hepatitis and HIV serology from Day -1 and added to screening; added weight to be assessed on Day 1; and, added footnote f next to “Laboratories: Urinary drug screen” defined below the table as “Methadone will be tested at screening only.” All subsequent footnote letters reordered accordingly.
2. Section 1, Table 1, footnote h, Section 8.1 (Screening Day -14 to Day-1), and Section 10.2 (Clinical Laboratory Tests): revised the statement regarding FSH testing as follows: removed “performed only at screening,” and added “required for postmenopausal women.”
3. Section 3.2 (Secondary Objectives/Endpoints: Removed secondary endpoint “Absolute change and percent change in C-P, MELD, Conn, and HESA scores.
4. Section 8.1 (Screening Day -14 to Day-1), added the following text to Urinary Drug Screen: “including a screen for methadone at screening only.”

- 
5. Section 4.2 (Study Design Rationale), changed text in the study design rationale from “...to correlate the plasma AMM reduction with dosing regimen administered...” to ‘...to characterize the PK/PD of MNK6106 in subjects.’”
  6. Section 5.2 (Exclusion Criteria), exclusion criterion #7 replaced “gastrointestinal hemorrhage” with “gastrointestinal bleeding.”
  7. Section 5.2 (Exclusion Criteria), exclusion criterion #8: replaced “estimated glomerular filtration rate” with “creatinine clearance calculated using the Cockcroft-Gault formula.”
  8. Section 5.2 (Exclusion Criteria), exclusion criterion #13, changed ‘psychiatric disorders’ to psychotic disorders “
  9. Section 10.2 (Clinical Laboratory Tests), added “FSH test (required for postmenopausal women).”
  10. Table 6 (C-P Classification for Severity of Liver Disease), removed incorrect table (former Table 10-4) and replaced with the correct table in former Section 10.8 (C-P Score).

Additional changes were made for formatting, spelling, punctuation, and clarification throughout protocol.

### **Protocol Amendment 1 – Summary of Changes**

The first amendment to the protocol was implemented to incorporate FDA requested changes and to correct oversight. Additional changes were made for clarification, to correct typos and certain hyperlinks, and for format errors. Detailed protocol changes are summarized below.

1. Included CTCAE (Common Terminology Criteria for AEs). Section 7.1, pg 36, Section 10.3.3, pg 58 and Section 10.7, pg 63 were revised.
2. Included INR as part of the laboratory assessments. Section 10.5, pg 61, Section 10.6.3, pg 62, Table 10.4, pg 63 and Section 10.8, pg 64 were revised.
3. Included the MELD score as part of the daily assessments. Section 8.1, pg 39, Section 8.3, pg 40 and Section 8.4, pg 41 were revised.
4. Included the MELD score as part of the exclusion criteria. Section 5.2, pg 28 was revised.
5. Included waist circumference at screening, Day 1 and last assessment in the clinic on Day 6. Table 1-1, pg 16 and Section 8.3, pg 39 were revised.
6. Added FSH testing for postmenopausal women. Table 1-1, pg 16 and Section 8.1, pg 39 were revised.
7. HESA score assessment was added at screening and every day during confinement. Table 1-1, pg 16, and Section 8.3, pg 40 were revised.
8. Child-Pugh and Conn score assessments were added at screening and every day. Table 1-1, pg 16, Section 8.1, pg 39, Section 8.3, pg 40 and Section 8.4, pg 41 were revised.

- 
9. Harmonized all liver and neurological assessments throughout the protocol. Former sections 8.5 and 9.4.1 were moved to Section 10.6.
  10. Eliminated the upper limit of ammonia levels in inclusion criterion #5. Section 5.1, pg 27, inclusion criterion #5 was revised.
  11. Removed remission of hepatic encephalopathy at enrollment (Conn score 0/1). Section 5.1, pg 27, former inclusion criterion #8 was deleted.
  12. Added an exclusion criterion for HESA Grade 4. Section 5.2, pg 28, was revised to add exclusion criterion #6.
  13. Clarify language of exclusion criterion words "therapy or". Section 5.2, pg 28, exclusion criterion #11 was revised.
  14. Added an exclusion criterion of "Has a history of prior cognitive impairment". Section 5.2, pg 28, exclusion criterion #12 was added.
  15. Added an exclusion criterion of: History of psychiatric disorders including but not limited to schizophrenia, dementia or other severe psychiatric disorders that would interfere with evaluation of HE. Section 5.2, pg 28, exclusion criterion #13 was added.
  16. Added an exclusion criterion of "Positive screening results for drugs and alcohol. (except for subjects positive to cannabinoids)". Section 5.2, pg 28, exclusion criterion #14 was added.
  17. Added text under Sedatives, "Any psychoactive agents including strong analgesics, antidepressants, and/or anxiolytics should be avoided such as but not limited to methadone." Section 6.5.1.1, pg 34, second paragraph, was revised
  18. Removed text in Meals and Fluids, "Water will be provided ad libitum except for 1 hour before and 2 hours after dosing". Section 6.5.3, pg 35 was revised to delete the sentence.
  19. Changed text in Meals and Fluids to remove "but." Section 6.5.3, pg 35, third paragraph was revised.
  20. Text for HESA Score was revised to add further explanation. Section 9.5, pg 49 was revised.
  21. Added prothrombin time/INR to clinical laboratories section. Section 10.2, pg 55 was revised.
  22. Added text to clarify CTCAE v5.0. Section 10.7, pg 63 was revised to add a link to current CTCAE information.
  23. Added a link under liver function clarification for the previous language for MELD and C-P scores. Links to Section 10.6 were added to Section 9.3.4 and Section 9.4, pg 49.
  24. Changed the methadone collection to screening only. Section 8.1, pg 38 was revised regarding urinary drug screen for methadone; Section 10.2, Urine Drug of Abuse and Alcohol Screen, pg 55 was revised to add methadone at screening.
-

25. Added a new section for AEs of special interest. Section 10.3.5, pg 60 was added as a new section.
26. A new secondary endpoint was added: Absolute change and percent change in C-P, MELD, Conn and HESA scores. Section 1.1, Secondary Endpoints, pg 13 and Section 3.2, Secondary Objectives/Endpoints, pg 24 were revised.
27. Added “active control” to study design description. Section 1.1, Overall Design, pg 14 and Section 4.1, Overall Design, pg 24 were revised.
28. Changed Day 5 to Day 5/ET globally.
29. Clarified the rescreening text to read “Subjects may be rescreened for a subsequent episode of acute HE, provided that the subject was not randomized. All Screening Visit procedures must be repeated”. Section 5.4, Screen Failures, pg 30 was revised.
30. Deleted the PD population since it is included in the mITT population. Section 9.2, Populations for Analysis, pg 48 was revised.
31. Both pretreatment and treatment-emergent periods were added to safety summaries. Section 9.3.3, Safety Analyses, pg 49 was revised.
32. Analysis methods were added for C-P, MELD, Conn and HESA scores. A new section 9.3.4, pg 49 was created.
33. Analysis of treatment compliance was added. Section 9.5.1, pg 50 was revised.
34. Added amendment date to title page and revised the page headers to indicate incorporation of amendment #1.

---

**LIST OF ABBREVIATIONS**

Abbreviation	Term
AE	Adverse event
AESI	Adverse event of special interest
AMM	Ammonia
CFR	Code of Federal Regulations
CNS	Central nervous system
COVID-19	Coronavirus disease 2019
C-P	Child-Pugh
CTCAE	Common Terminology Criteria for AEs
ECG	Electrocardiogram
eCRF	Electronic case report form
ET	end of treatment
FDA	Food and Drug Administration (US)
FSH	follicle stimulating hormone
GCP	Good Clinical Practices
HCV	Hepatitis C virus
HE	Hepatic encephalopathy
HESA	Hepatic Encephalopathy Scaling Algorithm
HIPAA	Health Insurance Portability and Accountability Act
HIV	Human immunodeficiency virus
HRT	hormonal replacement therapy
ICF	Informed consent form
ICH	International Council for Harmonisation
ID	Identification
IEC	Independent Ethics Committee
INR	International Normalized Ratio
IR	Immediate release
IRB	Institutional Review Board

---

---

Abbreviation	Term
IV	Intravenous
mITT	Modified intent-to-treat
MedDRA	Medical Dictionary for Regulatory Activities
MELD	Model for End Stage Liver Disease
MM	Medical monitor
MNK6105	L-Ornithine phenylacetate intravenous solution
MNK6106	L-Ornithine phenylacetate tablets
ORN	L-Ornithine
PAA	Phenylacetate
PAGN	Phenylacetylglutamine
PD	Pharmacodynamic
PK	Pharmacokinetic
PT	Prothrombin time
QTcF	QT interval corrected using Fridericia's formula
SAE	Serious adverse event
ULN	Upper limit of normal
US	United States

## 1. PROTOCOL SUMMARY

### 1.1. Synopsis

Study Title: A Randomized, Open-Label, Phase 2a Comparator Study to Assess the Pharmacodynamics, Safety and Pharmacokinetics of Oral Administration of MNK6106 (L-Ornithine Phenylacetate) Versus Rifaximin in Subjects With Hepatic Cirrhosis and a History of Prior Episodes of Hepatic Encephalopathy	
Protocol Number: MNK61062107	Type: Interventional/Phase 2a
Condition/Disease: Hepatic Cirrhosis and a History of Prior Episodes of Hepatic Encephalopathy	
Approximate Number of Subjects: 48	Approximate Duration of Subject Participation: 6 weeks

Rationale:
 
Current treatment strategies for the prevention of overt hepatic encephalopathy (HE) are limited to the correction or removal of precipitating factors, as well as the imperfect reduction of circulating ammonia (AMM) levels by dietary changes and/or pharmacological approaches. Pharmacological approaches include non-absorbed disaccharides (eg, lactulose) and antibiotics (eg, neomycin and rifaximin), which target AMM absorption and change the gut microbiome to non-urease-producing bacteria reducing intestinal AMM production, respectively. Lactulose is orally/rectally administered, does not directly target AMM metabolism, has limited efficacy in subjects with acute episodes of overt HE, is difficult to administer, and requires doses taken frequently throughout the day.
 
Rifaximin is indicated for reduction in risk of overt HE recurrence in patients at least 18 years of age. In the trials of rifaximin for HE, 91% of the subjects were using lactulose concomitantly. Differences in the treatment effect of those subjects not using lactulose concomitantly could not be assessed.
 
In the Phase 1/2a study OCR002-SP103, which was conducted with the oral formulation of MNK6106 (L-Ornithine phenylacetate tablets) although the percentage change in blood AMM concentrations was highly variable, MNK6106 dosing of 4 g and 7 g 3 times daily was seen to lower AMM concentrations or at least prevent increases in AMM concentrations following the discontinuation of lactulose.
 
MNK6105 (Intravenous formulation of L-Ornithine phenylacetate) has been evaluated in 2 Phase 1 studies OCR002-HV201 (healthy subjects) and OCR002-HE201 (subjects with Child-Pugh Class A or B cirrhosis and in 2 investigator initiated Phase 2 studies OP-GIB (subjects with cirrhosis and active gastrointestinal bleeding) and OCR002-HE209 (subjects with cirrhosis and HE). In the recently completed OCR002-HE209 study with MNK6105 (10 g/day, 15 g/day, and 20 g/day IV for 5 days), data suggested better clinical improvement, plasma AMM-lowering/normalizing pharmacodynamics (PD) effects ratio and decrease in AMM concentrations in subjects receiving MNK6105 compared to placebo.
	
Objectives and Endpoints:	
Primary Objective	Endpoint
To evaluate the pharmacological activities through plasma AMM concentration as a PD marker following oral administration of MNK6106 with rifaximin as a comparator in subjects with hepatic cirrhosis and a history of prior episodes of HE.	Absolute and percentage change of plasma AMM from baseline.

[figure not shown]
Study Title: A Randomized, Open-Label, Phase 2a Comparator Study to Assess the Pharmacodynamics, Safety and Pharmacokinetics of Oral Administration of MNK6106 (L-Ornithine Phenylacetate) Versus Rifaximin in Subjects With Hepatic Cirrhosis and a History of Prior Episodes of Hepatic Encephalopathy	
Protocol Number: MNK61062107	Type: Interventional/Phase 2a
Secondary Objectives	Secondary Endpoints
To determine the safety and tolerability of MNK6106 following oral administration of MNK6106 in subjects with hepatic cirrhosis and a history of prior episodes of HE.	Adverse event (AEs) and serious adverse event (SAEs).
To evaluate the exposure response (PD and safety) relationships following the oral administrations of MNK6106 in subjects with hepatic cirrhosis and a history of prior episodes of HE.	Plasma exposure of phenylacetate (PAA), L-ornithine (ORN) and phenylacetylglutamine (PAGN) with AMM reduction, and total renal elimination of PAGN.  PAA exposure and neurotoxicity.
Outcome Measures	
Outcome measures are identified to facilitate trial registration and patient access to basic results disclosed on public registries.	

 
The primary outcome measure in the study is the number of participants with a change in ammonia at Day 5.
 
The secondary outcome measure in the study is the number of participants with adverse events or deaths during the study.
 
	
Overall Design:	

This is a randomized, open-label, parallel group, multiple-dose, dose-ranging, active control, Phase 2a study. The objective of the study is to assess the PD, safety and pharmacokinetics (PK) of different doses of MNK6106 (oral administration) vs rifaximin in subjects 18 to 80 years of age (inclusive) with hepatic cirrhosis and a history of prior episodes of HE.
 
Approximately 48 subjects will be randomized to meet the primary objective. Subjects may participate in the study for a total of up to approximately 6 weeks, including a screening period of up to 28 days, a treatment period of 1 week (5 days), and a final visit 7 days (+ 3 day window) after ending study treatment.
 
The final visit window may be extended, due to extenuating circumstances, to 14 days after discussion with the Sponsor.
 
Subjects will be confined to the study center overnight during the 5-day treatment period and randomly assigned to receive 1 of 3 dosing regimens of MNK6106 or the comparator rifaximin for 5 days.
 
Approximately 48 subjects will be 1:1:1:1 randomized to 1 of the 4 groups. Subjects will receive either 1 of 3 MNK6106 dosing regimens (2 g three times daily, 4 g twice daily, or 4 g three times daily) or rifaximin (550 mg twice daily) taken orally for 5 days. Samples for plasma AMM levels will be drawn at screening and on Days 1, 3 and 5/ET, predose in the morning immediately before breakfast and 4 hours (<math>\pm 15</math> minutes) after the morning dose, as well as at the final visit 1 week (7 days [+ 3 day window] after the last dose). Samples for plasma PAA, ORN and PAGN will be drawn prior to the first dose on Day 1 (within 15 minutes prior to the morning dose) and then prior to (within 10 minutes) and 1 hour (<math>\pm 15</math> minutes) after the last dose on Days 1, 3, and 5/ET. Subjects will remain in the clinic overnight during Day 5/ET and be discharged on Day 6 after the last 24 hour urine collection is completed.
 
Approximately 1 week after the end of the treatment period, subjects will complete a final visit.
	

---

Study Title: A Randomized, Open-Label, Phase 2a Comparator Study to Assess the Pharmacodynamics, Safety and Pharmacokinetics of Oral Administration of MNK6106 (L-Ornithine Phenylacetate) Versus Rifaximin in Subjects With Hepatic Cirrhosis and a History of Prior Episodes of Hepatic Encephalopathy	
Protocol Number: MNK61062107	Type: Interventional/Phase 2a
Number of Subjects: Approximately 48 subjects will be randomized to meet the primary objective. Subjects may participate in the study for a total of up to approximately 6 weeks, including a screening period of up to 28 days, an treatment period of 1 week (5 days), and a final visit to occur 1 week (7 days [+ 3 day window]) after ending study treatment.	
Treatment Groups and Duration: All treatment groups will be dosed orally as follows: Group A: MNK6106 2 g (2 tablets), three times daily for 5 days (6 g daily dose and 30 g total dose). Group B: MNK6106 4 g (4 tablets), twice daily for 5 days (8 g daily dose and 40 g total dose). Group C: MNK6106 4 g (4 tablets), three times daily for 5 days (12 g daily dose and 60 g total dose). Group D: Rifaximin 550 mg tablet (1 tablet), twice daily for 5 days (1.1 g daily dose and 5.5 g total dose).	

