## 2. INTRODUCTION

MNK6106 is a novel ammonia (AMM)-lowering agent that uses pathways of AMM removal to reduce plasma AMM concentration in subjects with varying degrees of hepatic encephalopathy (HE).

MNK6106 (ornithine phenylacetate), in the form of the L-ornithine (ORN) salt of phenylacetate (PAA), is a single new chemical entity that allows for alternative pathways for the excretion of AMM in the setting of cirrhosis through the enhanced elimination of AMM ([Jalan et al, 2007](#)). L-ornithine stimulates the activity of glutamine synthetase, inducing body muscle to trap circulating AMM in the form of glutamine, which is a nontoxic carrier of AMM. Glutamine is then conjugated with PAA to form PAGN, which is excreted in urine. This strategy prevents the eventual recirculation and degradation of glutamine by glutaminase and avoids re-formation of AMM.

L-Ornithine phenylacetate was granted orphan drug status in 2010 by the US Food and Drug Administration (FDA); for the treatment of hyperammonemia and associated hepatic encephalopathy in patients with acute liver failure or acute or chronic liver disease.

A detailed description of the chemistry, pharmacology, efficacy, and safety of products containing L-Ornithine phenylacetate is provided in the Investigator's Brochure ([Mallinckrodt, 2019](#)).

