#### **9.3.1. Pharmacodynamic Analyses**

The descriptive statistics for PD variables, which are the plasma AMM level and the change of the plasma AMM level from baseline, will be used by treatment and by visit. The Mallinckrodt treatments will also be combined for display. The summaries will be based on the mITT population.

For continuous variables, descriptive statistics will include the following: the number of subjects reflected in the calculation (n), mean, median, standard deviation, minimum, and maximum. The 95% confidence intervals will be presented.

The graphic for PD variables by treatment and by visit will also be provided.

---

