### 9.3.2. Pharmacokinetic and Pharmacodynamic Analyses

The descriptive statistics for concentrations of PAA, ORN and PAGN will be used by treatment and by PK sampling time. Urinary recovery of PAGN will be summarized by treatment and study day. Descriptive statistics will include the following: the number of subjects reflected in the calculation (n), mean, median, standard deviation, minimum, and maximum. The 95% confidence interval will be presented.

Population PK modeling will be developed with the PK data obtained from the study such as concentration of PAA, ORN and PAGN. Sources of variability contributing to the PK will be identified. Exposure response relationships describing the safety and AMM levels following treatment with MNK6106 will be explored.

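### A dose-ranging trial plans no baseline-adjusted ammonia contrast among its randomised regimens, while its exposure-response objective rests on non-randomised exposure with no adjustment specified

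*Combined protocol and SAP*

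**What the plan says.** The synopsis (Overall Design) states: "This is a randomized, open-label, parallel group, multiple-dose, dose-ranging, active control, Phase 2a study". Allocation is 1:1:1:1 among 2 g tid (Group A), 4 g bid (B), 4 g tid (C) and rifaximin (D). Section 2.3 says that the appropriate MNK6106 dose is still undetermined.

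**Ammonia by randomised regimen.** Section 9.3.1 gives descriptive statistics for ammonia and its change "from baseline, will be used by treatment and by visit", with 95% confidence intervals, graphics and a display that pools the MNK6106 arms. It has no between-regimen estimate and no baseline covariate.

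**Adverse events by randomised regimen.** Section 9.5.1 summarises them by treatment group.

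**Clinical scores.** Section 9.5 does plan modelling for Child-Pugh, MELD, Conn and HESA: analysis of covariance after multiple imputation, and a Cochran–Mantel–Haenszel test stratified by baseline category.

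**Exposure-response.** The synopsis gives this secondary objective as "To evaluate the exposure response (PD and safety) relationships following the oral administrations of MNK6106 in subjects with hepatic cirrhosis". The safety endpoint under this objective is "PAA exposure and neurotoxicity". The response analysis in Section 9.3.2 is one sentence: "Exposure response relationships describing the safety and AMM levels following treatment with MNK6106 will be explored". It follows two sentences about pharmacokinetics: "Population PK modeling will be developed with the PK data obtained from the study such as concentration of PAA, ORN and PAGN" and "Sources of variability contributing to the PK will be identified". No response model, exposure metric or response covariate is named.

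**The concern.** Regimen is randomised; a subject's plasma level is not, whether it is measured or derived from the population PK model. If sicker subjects have higher levels and also a poorer ammonia response or more CNS symptoms, a concentration-response slope picks up severity as well as drug.

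The safety side is the more exposed, because the outcome terms overlap with signs of the disease. The CNS events of special interest in Section 10.3.5 include somnolence, disorientation and impaired memory. Somnolence and disorientation also appear in the Conn grades (Section 10.6.1) and on the HESA sheet (Section 10.8), which lists amnesia for recent events as well. Entry admits HESA Grades 0 to 3 and MELD up to 25, with no Child-Pugh limit (Section 5.2).

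At stake is how the trial informs dose. A comparison of randomised regimens is not subject to this confounding, but for ammonia the plan stops at separate arm summaries. A reader who wants to know what doubling the unit dose or adding a third daily dose does to ammonia must compare arms by eye, without adjustment for baseline.

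**Working it through.** **Step 1. Plan's own figures.** 48/4 = 12 per arm, so at most 3 × 12 = 36 subjects contribute MNK6106 exposure-response data. Daily doses are 2×3 = 6 g, 4×2 = 8 g and 4×3 = 12 g, which agree with Table 2. Section 9.1 gives no power, effect size or SD, so 48 cannot be derived from a formula; no sample-size figure is in dispute.

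**Step 2. What the randomised contrasts isolate.** C minus A is 4 g against 2 g, both tid. C minus B is tid against bid, both at 4 g. Each changes one feature of the regimen.

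**Step 3. Precision.** In units of the between-subject SD of the response:
- one arm: 2.201/√12 = 0.64
- difference, 12 v 12: 2.074 × √(2/12) = 0.85

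Baseline adjustment narrows the second figure by an amount that depends on the correlation of response with baseline, which the documents do not give.

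**Step 4. How much exposure variation is randomised.** The variance of ln(6), ln(8), ln(12) is 0.0808 (SD 0.284). For an assumed between-subject exposure CV, the log-scale variance is s² = ln(1 + CV²), and the share due to randomised dose is 0.0808/(0.0808 + s²).

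| Assumed CV | Share due to randomised dose |
|---|---|
| 30% | 48% |
| 50% | 27% |
| 70% | 17% |

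For CV 50%: s² = ln(1.25) = 0.2231, and 0.0808/0.3039 = 27%. At each assumed CV, at least about half of the variation is not randomised.

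**Step 5. Size of possible bias.** Let log exposure = log dose + b·S + error and response = g·S + error (SD 1), where S is standardised severity. The true exposure effect is zero. If severity explains a fraction f of s², then b = √(f·s²), and the expected unadjusted slope is g·b/(0.0808 + s²).

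Worked case (CV 50%, f = 25%, g = 0.5): b = √0.0558 = 0.236, and the slope is 0.5 × 0.236/0.3039 = 0.39 residual SD per log unit.

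Simulation, 36 subjects, 4,000 runs per case, nominal 5%, CV 30–70%, g = 0.3–0.5:

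| Analysis | f = 25–50% | f = 0 |
|---|---|---|
| Exposure alone: expected bias | 0.20 to 0.62 | 0 |
| Exposure alone: false significance | 9% to 41% | 4.6% to 5.7% |
| Exposure plus severity | 4.5% to 5.6% | 4.4% to 5.7% |
| Randomised dose | 4.7% to 5.4% | 4.5% to 5.2% |

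Severity is taken here as measured without error; a noisy score would leave some bias. CV, f and g are assumptions, because the documents give none of them. Significance serves only as a measure of bias; the plan has no exposure-response test.

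**The case against.** **The randomised comparison is not ignored.** Ammonia is summarised by arm with confidence intervals and adverse events by arm, and the clinical scores are modelled. A reader might infer that exposure-response is the only response analysis planned; Sections 9.3.1, 9.5 and 9.5.1 show otherwise. What is missing is the ammonia contrast itself.

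**Silence is not exclusion.** Section 9.3.2 leaves response covariates unnamed and does not rule them out. It plans population PK modelling and a search for sources of PK variability. Section 9.5.2 refers to a statistical analysis plan, though only for exposure periods, and fuller modelling text may exist elsewhere. A reader might infer that the analysis is confounded; the documents support only that it is open to confounding.

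**The overlap with encephalopathy is partly handled.** Treatment-emergent events must be new or worsened. Conn and HESA are recorded daily during treatment. Section 10.3.5 requires onset times, narratives and individual PK values for CNS events. This removes stable baseline signs from the treatment-emergent count. It does not separate worsening encephalopathy from a drug effect in a concentration-response relation.

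**Body size and renal function.** Doses are fixed grams, ammonia is trapped in muscle ("inducing body muscle to trap circulating AMM in the form of glutamine", Section 2) and PAGN leaves in urine, so a reader might infer that weight and renal function are further confounders. The documents do not show it. Weight is not muscle mass, nothing links low weight to poorer ammonia response, and the renal argument concerns PAGN, whereas neurotoxicity is tied to PAA.

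**The numbers depend on assumptions.** This stands. With stronger inputs (log exposure +0.5 and log ammonia change +0.30 per SD of severity, residual SDs 0.3 and 0.35) false significance reaches 89%. That requires severity to explain 0.25/(0.25 + 0.09) = 74% of between-subject exposure variance and 0.09/(0.09 + 0.1225) = 42% of the variance in ammonia change. With weak inputs (0.1 and 0.05) it is about 5%. The documents support none of these values.

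**The study is exploratory**, with no hypothesis to test (Section 9.3). That limits the importance of the point. It does not remove bias from an estimate, and an adjusted contrast with an interval requires no hypothesis test.

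**Conclusion.** The point holds in a limited form. For ammonia, a trial described as dose-ranging plans no between-regimen estimate and no baseline adjustment, although it plans analysis of covariance for its clinical scores. Its exposure-response objective uses non-randomised exposure without stating how severity or baseline encephalopathy will be handled.

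The size of any confounding is unknown. Under moderate assumptions (severity explaining 25–50% of between-subject exposure variance and shifting response by 0.3–0.5 residual SD), an unadjusted slope is falsely significant in 9% to 41% of trials. The bias is nil if severity does not affect exposure. The overlap between CNS event terms and encephalopathy signs does not depend on those assumptions.

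This limits the interpretation of a secondary, exploratory objective. It does not invalidate the primary summaries, and it is worth correcting because the correction is cheap.

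**What to change.** 1. In Section 9.3.1, add an exploratory analysis of covariance of the log ratio of post-baseline to baseline ammonia, with regimen and log baseline ammonia as terms. Report estimates and 95% confidence intervals for C minus A and C minus B.
2. Tabulate the CNS events of special interest, as a group and by term, by randomised regimen.
3. In Section 9.3.2, keep the exposure-response objective, name the exposure metric and state a short covariate set: baseline ammonia plus one liver-severity score (Child-Pugh or MELD) for ammonia; baseline HESA for CNS events.
4. Present concentration-response results beside items 1 and 2, labelled non-randomised.

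**Cost.** A few lines of text and a little more analysis. The schedule of events already collects every input. The contrasts will be imprecise (about ±0.85 SD before adjustment) and should be read as estimates. With at most 36 subjects, and no replacement of those who discontinue, a longer covariate list would be fragile.
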